2.2.5.1. Cardiac Safety

A cardiodynamic evaluation of healthy participants in the MAD portion of Study 207187 [GSK Document Number [2020N430256_00](#)] (placebo or GSK3640254 dose range 50 to 320 mg daily for 14 days) was performed. Serial ECGs were extracted from continuous Holter monitors at time-matched baseline on Day -1 and for approximately 24 hours post-dose on Days 1 and 14. There were no abnormal clinically significant arrhythmias or QT prolongations (values >500 ms or increases >60 ms from baseline) observed for any participant in the SAD or MAD cohorts. In the concentration-corrected QT interval (C-QTc) analysis, a final model with a treatment effect-specific intercept reasonably represented the data. The slope of the C-QTc relationship was 0.004 ms per ng/mL (90% confidence interval [CI]: 0.0023 to 0.0048) with a small treatment effect-specific intercept of -0.9 ms (90% CI: -4.47 to 2.69). The QT effect (placebo-corrected change from baseline in QTcF [$\Delta\Delta\text{QTcF}$]) of GSK3640254 could be predicted to be 5.38 ms (90% CI: 1.66 to 9.10) and 6.70 ms (90% CI: 2.79 to 10.61) for the 200 mg (1779 ng/mL) and 320 mg (2154 ng/mL) doses, respectively, on Day 14. Based on this C-QTc analysis, a QTc using the Fridericia formula (QTcF) effect above 10 ms could be excluded in GSK3640254 plasma concentrations of up to approximately 2000 ng/mL (corresponding to doses approximately \leq 200 mg QD).

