4.3. Justification for Dose

A single dose of GSK3640254 will likely not be able to achieve therapeutic or supratherapeutic exposures; thus, multiple-dose administration will be needed. A projected therapeutic dose of 100 mg GSK3640254 was selected for this study (the dose range in a planned Phase 2b dose range finding study in HIV-1 infected adults is 100 to 200 mg QD). The initial planned dose for Part 1 was selected based on a population PK model referenced on the single-dose (1 to 400 mg) and multiple-dose (50 to 320 mg QD for 14 days) data from healthy participants from the FTIH study 207187, as well as the multiple-dose data in HIV-1 infected participants (10 to 200 mg QD for 7 to 10 days). The PK of GSK3640254 (given with food) was described by a two-compartment model with sequential zero-order absorption (in the depot compartment) followed by first order absorption (from depot to the central compartment) and first order elimination. Weight was found to be a significant covariate on K_a . In addition, study (as a surrogate for subject type and differences in GSK3640254 salt formulations between the 2 studies) was also found to be significant covariates on bioavailability (F was ~27% lower in the FTIH Study 207187 compared to that from the proof of concept Study 208132).

As indicated in Section 4.2, the supratherapeutic dose of GSK3640254 has not been determined. The target supratherapeutic exposure (steady-state Cmax) is approximately 4.4 μ g/mL, which provides approximately 4-fold cover for 100 mg QD therapeutic dose, 2-fold for 200 mg QD, 1:1 for inhibitors with a 200 mg dose or 2:1 with 100 mg dose (assuming an increase in exposure with CYP-inhibitors of approximately 2-fold).

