9. STATISTICAL CONSIDERATIONS

9.1. Statistical Hypotheses

There is no formal statistical hypothesis to be tested in Part 1.

For Part 2, the statistical hypothesis to be tested for the primary assessment of QT prolongation at the highest clinically relevant exposure using the C-QTc analysis for each active dose group is:

$$H_0: \Delta\Delta QTcF \geq 10 \text{ ms}$$

$$H_1: \Delta\Delta QTcF < 10 \text{ ms}$$

where $\Delta\Delta QTcF$ is the mean $\Delta\Delta QTcF$ at the mean Cmax for each active dose group, respectively.

In addition, the statistical hypothesis to be tested for the assay sensitivity using the C-QTc analysis is:

$$H_0: \Delta\Delta QTcF \leq 5 \text{ ms}$$

$$H_1: \Delta\Delta QTcF > 5 \text{ ms}$$

where $\Delta\Delta QTcF$ is the mean $\Delta\Delta QTcF$ at the mean Cmax for the moxifloxacin group.

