9.2. Sample Size Determination

Part 1: A total of up to 16 participants are planned to be randomized, 8 participants per cohort (6 participants to receive GSK3640254 and 2 participants to receive placebo). For

Part 1, as there is no formal research hypothesis being statistically tested, the sample size is not selected based on statistical considerations but was determined using feasibility.

Part 2: A sample size of approximately 42 participants is chosen to obtain 34 evaluable participants to complete the study. A sample size of 34 evaluable participants will provide more than 90% power to exclude that active drug causes more than a 10-ms QTc effect at clinically relevant plasma levels, as shown by the upper bound of the 2-sided 90% CI of the model predicted QTc effect ($\Delta\Delta QTcF$) at the observed geometric mean Cmax of active drug in the study.

This power is estimated approximately using a paired t-test. The calculation assumes a one-sided 5% significance level, an underlying effect of GSK3640254 of 4 ms and a standard deviation (SD) of the ΔQTc of 8.5 ms for both active drug and placebo. [Table 2](#) provides the sample sizes for power of 90% and 95% with underlying effect of 3, 4, and 5 ms and SD of 8, 8.5, and 9.5 ms.

The C-QTc analysis method is supported by [Darpo, 2015](#) and [Ferber, 2015](#) and consistent with the experiences from 25 recent TQT studies in ERT, which provided SD=8 ms as a conservative estimate for general TQT studies. Note that this calculation is conservative also because it does not take into account any gain in precision due to the use of all data of each participant with the help of a linear mixed effects model. An SD of 9.5 ms is a conservative value used in previous MI compound BMS-663068 and AI compound Fostemsavir TQT studies in GSK. In the previous GSK3640254 FTIH Study 207187 SAD/MAD study, the within-participant SD based on by-time point analysis was 8.5 ms, which provides the conservative estimated SD for this compound. Therefore, the underlying effect 4 ms and SD=8.5 ms with 90% of power for the study sample size of 34 participants was chosen for this study. With the dropout rate of 20%, approximately 42 participants will be enrolled to ensure the evaluable number of participants is greater or equal to 34.

Table 2 Sample Size Determination - Power

Sample size	Number of Participants for 90% Power	Number of Participants for 95% Power
Underlying effect 3 ms SD = 8 ms	22	28

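### The power above 90% in Section 9.2 is conditional on a 4 ms effect tied to no exposure, and does not extend to the supratherapeutic hypothesis in Section 9.1

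*Protocol*

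**What the plan says.** - **Hypotheses (Section 9.1).** The null is a placebo-corrected QTcF change of 10 ms or more, evaluated "at the mean Cmax for each active dose group, respectively". The supratherapeutic group is therefore a tested primary hypothesis alongside 100 mg.
- **Power (Section 9.2).** A sample of 34 evaluable participants, it says, "will provide more than 90% power to exclude that active drug causes more than a 10-ms QTc effect at clinically relevant plasma levels". The basis is a paired t-test at one-sided 5%, with "an underlying effect of GSK3640254 of 4 ms and a standard deviation (SD") of 8.5 ms on each treatment. Table 2 varies the inputs "with underlying effect of 3, 4, and 5 ms and SD of 8, 8.5, and 9.5 ms". The SD is sourced to Study 207187. The 4 ms is given no source, dose or concentration.
- **Prior model (Section 2.2.5.1, same study).** "The slope of the C-QTc relationship was 0.004 ms per ng/mL (90% confidence interval [CI]: 0.0023 to 0.0048"), with an intercept of -0.9 ms. The predicted effects were "5.38 ms (90% CI: 1.66 to 9.10) and 6.70 ms (90% CI: 2.79 to 10.61) for the 200 mg (1779 ng/mL"); the second of the two belongs to 320 mg, at 2154 ng/mL. A 10 ms effect "could be excluded in GSK3640254 plasma concentrations of up to approximately 2000 ng/mL".
- **Target (Section 4.3).** "The target supratherapeutic exposure (steady-state Cmax) is approximately 4.4" µg/mL, described as roughly 4-fold the 100 mg exposure and 2-fold the 200 mg exposure.
- **Conclusion rule (Section 9.4.1.2).** Predictions are made at each dose group's geometric mean Cmax. The closing sentence then draws a single drug-level conclusion at clinically relevant plasma levels, without saying which levels those are.

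**The concern.** Both printed predictions from the prior model exceed every effect in Table 2, and the supratherapeutic target is about twice the highest concentration with a printed prediction. A reader who takes Section 9.2 together with Section 9.1 would suppose that both dose-group hypotheses are powered at about 90%. The protocol's own data support that for the therapeutic dose only.

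Two things are at stake. The first is the stated operating characteristic of the primary analysis. The second is interpretation: a pass at the therapeutic Cmax with no pass at the supratherapeutic Cmax is foreseeable. As worded, the conclusion sentence would let the therapeutic pass alone be read as a negative finding for the drug.

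**Working it through.** **Inputs.** From Section 9.2: margin 10 ms, one-sided 5%, SD 8.5 ms per treatment, n = 34, effect 4 ms. From Section 2.2.5.1: the slope, intercept and two predictions quoted above. From Section 4.3: target 4400 ng/mL, hence 4400/4 = 1100 ng/mL for 100 mg and 4400/2 = 2200 ng/mL for 200 mg.

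**1. Reproduce the plan's figure.** n = 2 × 8.5² × (1.645 + 1.282)² / (10 − 4)² = 34.4, against 34 in Table 2. The same formula gives 49.5 for 5 ms, against 49. The standard error is 8.5 × √2 / √34 = 2.06 ms. Power at 4 ms is 89.7% by the normal approximation and 88.6% by the exact paired t (33 df). The arithmetic stands for its own inputs, though calling it more than 90% is slightly generous.

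**2. Recover the prior line.** Slope = (6.70 − 5.38) / (2154 − 1779) = 0.00352. Intercept = 5.38 − 0.00352 × 1779 = −0.88. Both agree with the printed, rounded values.
- 4 ms: (4 + 0.88) / 0.00352 ≈ 1390 ng/mL (1225 with the rounded slope 0.004).
- 10 ms: (10 + 0.88) / 0.00352 ≈ 3090 ng/mL. At the slope limits with the intercept held at −0.9: 10.9 / 0.0048 ≈ 2270 and 10.9 / 0.0023 ≈ 4740.

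**3. Allow for mixed-model precision (an assumption).** The assay-sensitivity paragraph of Section 9.2 reports a concentration-QTc SE of 1.24 ms with n = 24 and within-subject SD 5.4. The paired-t SE for those inputs is 5.4 × √2 / √24 = 1.56, so the ratio is 0.80. Applied here, the SE becomes 0.80 × 2.06 ≈ 1.64 ms. The ratio comes from moxifloxacin data and may not carry over.

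**4. Power by exposure, n = 34, central line.**

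| Concentration (ng/mL) | Effect (ms) | Paired t | With assumed gain |
|---|---|---|---|
| 1100 (implied 100 mg) | 2.99 | 95% | 99% |
| 1390 | 4.00 | 88.6% | 97% |
| 1779 (printed) | 5.38 | 71% | 87% |
| 2154 (printed) | 6.70 | 47% | 63% |
| 3090 | 10.0 | 5% | 5% |
| 4400 (target) | 14.6 | near 0 | near 0 |

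Over the printed 90% CIs, paired-t power runs from 99% to 11% at 1779 ng/mL and from 96% to 3% at 2154 ng/mL. At 1100 ng/mL the upper slope limit gives 0.0048 × 1100 − 0.9 = 4.38 ms and 85%. At 4400 ng/mL the lower slope limit gives 0.0023 × 4400 − 0.9 = 9.2 ms and 10%.

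**5. Where 90% is reached.** The paired t needs an effect of at most 3.84 ms: about 1340 ng/mL on the central line, and 990 to 2060 ng/mL over the slope limits. With the assumed gain the limit is about 5.1 ms, or about 1700 ng/mL on the central line.

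**6. Exposure at 200 mg.** Section 2.3.1 gives a mean Cmax of 1.4 µg/mL, Section 2.2.5.1 gives 1779 ng/mL, and Section 4.3 implies about 2200 ng/mL. On the central line these correspond to about 4.05, 5.38 and 6.86 ms.

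**The case against.** **The 4 ms is not arbitrary.** Section 2.3.1's 1.4 µg/mL for 200 mg, the top of the planned Phase 2b range, gives 4.05 ms on the central line. The effect may have been meant for the highest planned Phase 2b dose. That is a fair reading, but Section 9.2 does not say so, and the other two figures for 200 mg give larger effects.

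**The paired t is conservative.** Section 9.2 says so, and the assumed gain puts power at 4 ms at 97%. This stands, and it means 1340 ng/mL is not a hard limit. It does not rescue the supratherapeutic group: 6.70 ms still gives only 63%, and precision cannot help where the true effect is at or above the margin.

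**The condition is stated.** Section 9.2 names the 4 ms assumption and nowhere says that both groups are powered. If the true supratherapeutic effect exceeds 10 ms, failing to reject is correct behaviour, not a deficit. Both points hold. The fault is that the power sentence refers to active drug generally, while Section 9.1 tests each group.

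**High concentrations are extrapolated.** Linearity above 2154 ng/mL is not established, an Emax model is a planned fallback, the dose is not yet set, and single-dose exposure did not rise from 400 to 700 mg. All true. The results at 5.38 and 6.70 ms, however, need no extrapolation.

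**A split result would be visible.** Predictions are reported for each dose group, and detailed wording could sit in an SAP that is not shown. But the conclusion sentence is fixed in this protocol, and it is unqualified.

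**Conclusion.** The power statement is acceptable as a calculation conditional on 4 ms, and on central estimates it covers the 100 mg group (95%, though 85% at the upper slope limit). It does not extend to the supratherapeutic hypothesis. Paired-t power is 71% at 5.38 ms and 47% at 6.70 ms (87% and 63% with the assumed gain), and at most 5% wherever the true effect is 10 ms or more. The central line reaches 10 ms well below the 4400 ng/mL target. This rests on the Section 2.2.5.1 model, SD 8.5 ms and 34 evaluable participants.

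A reader might infer more than the documents support:
- That the sample size calculation is wrong: it reproduces.
- That the supratherapeutic comparison is bound to fail: the lower slope limit leaves 9.2 ms at the target, and the target may not be reached.
- That 90% power stops exactly at 1340 ng/mL: that is one point in a range of 990 to 2060 ng/mL by paired t.
- That the trial needs more participants: no sample size helps if the true effect is at or above the margin.

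**What to change.** **Section 9.2.**
- Say which exposure the 4 ms effect represents, and reconcile the three values for 200 mg (1.4 µg/mL, 1779 ng/mL, about 2200 ng/mL).
- Restate power by dose group, with the range from the printed CIs and slope limits.
- Give the exposure up to which about 90% holds as a range: about 1340 ng/mL by paired t (990 to 2060 over the slope limits), or about 1700 ng/mL with the assumed mixed-model gain.
- State that the figure does not apply to the supratherapeutic hypothesis.

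**Section 9.4.1.2.** Tie the conclusion of no clinically relevant prolongation to the dose-group geometric mean Cmax at which the upper bound is below 10 ms, so that a therapeutic pass alone does not give an unqualified statement about the drug.

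**Cost.** A few sentences in 9.2 and one in 9.4.1.2. Sample size, doses, conduct and model are unchanged. The stated power becomes less favourable for the supratherapeutic group.

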9.3. Populations for Analyses

The following populations are defined:

Population	Description
Screened	All participants who sign the ICF.
Randomized	All participants who are randomly assigned to a treatment/treatment sequence.
Safety	All randomized participants who receive at least 1 dose of study intervention. Participants will be analysed according to the intervention they actually received. This population will be used for all demographic and safety summaries.
QT/QTc	The QT/QTc population will include all participants in the safety population with measurements at baseline as well as on-treatment with at least 1 post-dose time point with a valid $\Delta QTcF$ value. The QT/QTc population will be used for the by-time point assay sensitivity, and categorical analyses of the cardiodynamic ECG parameters.
PK Concentration	The PK Concentration Population will include all participants who undergo plasma PK sampling and have evaluable PK assay results. This population will be used for the PK concentration listings, summary tables, and plotting of concentration/time data.
PK Parameter	The PK Parameter Population will include all participants who undergo plasma PK sampling and have evaluable PK parameters estimated. This population will be used for PK parameter listings and summary tables.
PK/QTc	The PK/QTc Population will include all participants who are in both the QT/QTc and PK concentration populations with at least 1 pair of post-dose PK and QTcF data from the same time point as well as participants in the QT/QTc population who received placebo. The PK/QTc population will be used for the C-QTc analysis. The PK/QTc Population will be defined for GSK3640254 and for moxifloxacin.

9.4. Statistical Analyses

9.4.1. Cardiodynamic Analyses

9.4.1.1. QT Correction Methods

The QT and RR value for each beat will be used for HR correction. The primary HR correction method will be the Fridericia's correction (QTcF) defined as $QTcF \text{ (ms)} = QT \text{ (ms)} / [RR \text{ (ms)} / 1000]^{1/3}$ if there is no effect of GSK3640254 on HR.

If a substantial HR effect is observed (i.e., the largest least squares [LS] mean $\Delta\Delta HR$ is greater than 10 bpm in the by-time point analysis), other correction methods such as optimized HR-corrected QT interval (QTcI), and individual HR-corrected QT interval (QTcS) will be explored using the drug-free QT/RR data extracted from the full range of HR in the 24-hour Holter recording on Day -1. The method that removes the HR

dependence of the QT interval most efficiently will be chosen as the primary correction method. More details will be described in a separate statistical analysis plan.

9.4.1.2. Concentration-QTc Analysis (Primary Analysis)

The relationship between GSK3640254 plasma concentrations and $\Delta QTcF$ will be quantified using a linear mixed-effects modelling approach. The model will have $\Delta QTcF$ as the dependent variable, GSK3640254 plasma concentration as the exploratory variate (0 for placebo), centred baseline $QTcF$ (i.e., baseline $QTcF$ for individual participant minus the population mean baseline $QTcF$ for all participants in the same treatment period) as an additional covariate, treatment (active = 1 or placebo = 0) and time (i.e., post-dose time point) as fixed effects, and random intercept and slope per participant [Garnett, 2018]. An unstructured covariance matrix will be specified for the random effects. If convergence cannot be achieved even after appropriate rescaling of the concentrations, the random effect on the slope and intercept will be dropped, in this order, until convergence is achieved. The degrees of freedom of estimates will be determined by the Kenward-Roger method. From the model, the slope (i.e., the regression parameter for concentration) and the treatment effect-specific intercept (defined as the difference between active and placebo) will be estimated together with the 2-sided 90% CI. The estimates for the time effect will be reported with degrees of freedom and SE.

The geometric mean of the individual C_{max} values for participants in each of the active dose groups will be determined. The predicted effect and its 2-sided 90% CI for $\Delta\Delta QTcF$ (i.e., slope estimate \times concentration + treatment effect-specific intercept) at this geometric mean C_{max} of GSK3640254 will be obtained. If the upper bound of the 2-sided 90% CI of the predicted effect of $\Delta\Delta QTcF$ at clinically relevant plasma levels of GSK3640254 is below 10 ms, it will be concluded that GSK3640254 does not cause clinically relevant QTc prolongation.

The plot of the observed median-quantile GSK3640254 concentrations and associated mean placebo-adjusted $\Delta QTcF$ (i.e., $\Delta\Delta QTcF$) with 2-sided 90% CI adjusted for diurnal effects, together with the regression line presenting the predicted $\Delta\Delta QTcF$ (2-sided 90% CI) [Tornøe, 2011] will be used to evaluate the adequacy of the model fit to the assumption of linearity and the impact on quantifying the C-QTc relationship. The observed $\Delta QTcF$ values from the active group will be adjusted by the estimated time effect from the C-QTc model (i.e., the estimated diurnal effect under the placebo treatment). The individually estimated placebo-adjusted $\Delta QTcF_{i,j}$ equals the individual $\Delta QTcF_{i,j}$ for participant i administered GSK3640254 at time point j minus the estimation of time effect at time point j . For evaluation of the HR-corrected QT interval, a scatter plot and quantile plot of $QTcF$ and RR intervals by treatment with regression line and a linear mixed-effects line (90% CI), respectively, will also be given. Additional exploratory analyses (via graphical displays and/or model fitting) will include accounting for a delayed effect (hysteresis) and the justification for the choice of cardiodynamic model (linear versus nonlinear) as follows.

Hysteresis will be assessed based on joint graphical displays of the LS mean difference between $\Delta QTcF$ under GSK3640254 and under placebo ($\Delta\Delta QTcF$) for each post-dose time point from the by-time point analysis and the mean concentrations of GSK3640254

at the same time points. In addition, hysteresis plots will be given for LS mean $\Delta\Delta\text{QTcF}$ and the mean concentrations. If a QT effect ($\Delta\Delta\text{QTcF}$) >10 ms cannot be excluded in the by-time point analysis in the 2 active dose groups, and if the mean peak $\Delta\Delta\text{QTcF}$ effect is observed at the same time point in the by-time point analysis in the 2 active dose groups, and if a delay between peak $\Delta\Delta\text{QTcF}$ and peak plasma concentration in the plot ($\Delta\Delta\text{QTcF}$ versus GSK3640254) of more than 1 hour is observed in a consistent way for the 2 active dose groups, other C-QTc models, such as a model with an effect compartment, may be explored. With the provision stated above, hysteresis will be assumed if the curve of the hysteresis plot shows a counterclockwise loop. A significant treatment effect-specific intercept is not biologically plausible and therefore may be indicative of hysteresis or model misspecification, if it cannot be explained by a nonlinear relationship.

To assess the appropriateness of a linear model, normal Q-Q plots for the standardized residuals and the random effects, and plots of standardized residuals versus concentration, fitted values, centered baseline QTcF, nominal time, and active treatment will be produced. Scatter plots for standard residuals versus continuous covariates and box plots for standard residuals versus discrete covariates will be provided. The scatter plots of standardized residuals versus concentration and versus centered baseline QTcF by LOESS fitting (i.e., locally weighted scatter plot smoothing as described by [Cleveland, 1979]) will also be produced with optimal smoothing parameters selected by the Akaike information criterion with a correction (AICC [Hurvich, 1998]). A scatter plot of observed concentration and ΔQTcF with a LOESS smooth line with 90% CI and a linear regression line will also be provided to check the assumption of a linear C-QTc relationship. If there is an indication that a linear model is inappropriate, additional models will be fitted, in particular an Emax model. The C-QTc analysis will then be repeated for the model found to best accommodate the nonlinearity detected.

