4.2. Scientific Rationale for Study Design

The purpose of this study is to provide an assessment of the effects of GSK3640254 on the QT interval. The design of the study follows the general design principles outlined in

the E14 guidance for the clinical evaluation of the QT/QTc with non-antiarrhythmic drugs [DHHS, 2005]. Both a therapeutic dose and a supratherapeutic dose of GSK3640254 will be evaluated in the main QTc study. As the supratherapeutic dose of GSK3640254 has not been determined, this study will be conducted as an adaptive 2-part design, where projected doses will be identified and may be modified according to assessment of accrued data. In Part 1, a sentinel cohort will be used to determine the supratherapeutic dose. If needed, a second sentinel cohort employing BID dosing may be added.

In accordance with ICH E14, this study will be conducted in healthy participants to eliminate variables known to influence ECG parameters (e.g., concomitant medications or diseases). The sample size will accommodate a time-matched statistical analysis on the primary endpoint, and a positive-control group will be utilized to establish assay sensitivity. Further, the half-life of GSK3640254 (i.e., 22 to 28 hours) allows for a crossover design, wherein the participants will act as their own controls.

As outlined in the ICH E14 guideline, the study will use a randomized, partially double-blind (open label for moxifloxacin), placebo- and positive-controlled design. The positive control, moxifloxacin, will be used to confirm assay sensitivity for QTc prolongation. Moxifloxacin is a widely used positive reference substance for assaying the sensitivity of a TQT study to detect changes in the QTc interval at a single dose of 400 mg.

GSK3640254 will be administered under double-blind conditions to avoid bias. The central ECG laboratory will be blinded to dose consistent with FDA standards.

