8.6.2. Cardiodynamic Sample Analysis

The primary analysis will be based on C-QTc modeling of the relationship between GSK3640254 plasma concentration and change-from-baseline QTcF (Δ QTcF) with the intent to exclude an effect of $\Delta\Delta$ QTcF > 10 ms at clinically relevant plasma levels of GSK3640254.

In addition, the effect of GSK3640254 on placebo-corrected change-from-baseline in QTcF, HR, PR, and QRS ($\Delta\Delta$ QTcF, $\Delta\Delta$ HR, $\Delta\Delta$ PR, and $\Delta\Delta$ QRS) will be evaluated at each post-dose time point (“by-time point” analysis) using the intersection union test. An analysis of categorical outliers will be performed for changes in HR, PR, QRS, QTcF, T-wave morphology, and U-wave presence.

Assay sensitivity will be evaluated by C-QTc analysis of the effect on ($\Delta\Delta$ QTcF) of moxifloxacin using the same model as for the primary analysis. Assay sensitivity will be deemed met if the slope of the C-QTc relationship is statistically significant at the 10% level in a 2-sided test and the predicted QTc effect (i.e., the lower bound of the 2-sided 90% CI of $\Delta\Delta$ QTcF) is above 5 ms at the observed geometric mean Cmax of 400 mg moxifloxacin.

For all continuous ECG parameters from each period, baseline will be the average of the derived ECG intervals from the 3 ECG time points prior to dosing (-45, -30,

and -15 minutes) on Day 1 for the respective period. For T-wave morphology and U-wave presence, baseline includes any findings observed in any replicates from the 3 pre-dose time points (-45, -30, and -15 minutes) on Day 1 in each period.

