9.4.1.5. Assay Sensitivity

Assay sensitivity will be evaluated by C-QTc analysis of the effect on $\Delta\Delta\text{QTcF}$ of moxifloxacin using the same model as for the primary analysis. If the slope of the moxifloxacin plasma concentration/ ΔQTcF relationship is statistically significant at the 10% level in a 2-sided test and the lower bound of the 2-sided 90% CI of the predicted QTc effect at the geometric mean Cmax of the 400 mg dose is above 5 ms, assay sensitivity will be deemed to have been demonstrated.

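### The rule for concluding no clinically relevant QTc prolongation does not depend on assay sensitivity, and the protocol attaches no consequence to a failed moxifloxacin test

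*Protocol*

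**What the plan says.** Section 9.4.1.2 gives the decision rule for the primary analysis. If the upper bound of the two-sided 90% CI for the predicted effect at clinically relevant plasma levels "is below 10 ms, it will be concluded that GSK3640254 does not cause clinically relevant QTc prolongation". No second condition is attached.

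Assay sensitivity is treated separately:

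- Section 4.2 gives the purpose: "The positive control, moxifloxacin, will be used to confirm assay sensitivity for QTc prolongation".
- Sections 1.1 and 3 list it as a secondary objective of Part 2.
- Section 8.6.2 sets the criterion: "Assay sensitivity will be deemed met if the slope of the C-QTc relationship is statistically significant at the 10% level in a 2-sided test", together with a lower 90% bound above 5 ms at the geometric mean Cmax of moxifloxacin.
- Section 9.1 adds it after the primary hypothesis: "In addition, the statistical hypothesis to be tested for the assay sensitivity using the C-QTc analysis is" that the effect exceeds 5 ms.
- Section 9.2 sizes it on its own.
- Section 9.4.1.5 repeats the criterion and ends with: "assay sensitivity will be deemed to have been demonstrated".

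None of these places makes the negative conclusion depend on the moxifloxacin result, and none says what is concluded if moxifloxacin fails.

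**The concern.** An upper bound below 10 ms can arise in two ways: the drug has little effect, or the experiment registers less of the effect than is there. The positive control exists to tell these apart, and Part 2 spends one of its four periods on it. As the rule is worded, the result of that period cannot change the primary conclusion.

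The mechanism that matters is attenuation, meaning anything that shrinks measured effects towards zero. This is a one-sided exclusion test, so attenuation moves the result towards the safety claim. The case in which the rule gives an unsupported conclusion is therefore the case that the moxifloxacin arm was included to detect.

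**Working it through.** **Inputs (Section 9.2 unless noted).** 34 evaluable participants; margin 10 ms; assumed drug effect 4 ms; SD of the change from baseline 8.5 ms under both active drug and placebo; "The calculation assumes a one-sided 5% significance level". For moxifloxacin: true effect 10 ms, threshold 5 ms, reference-study SE 1.24 ms with n = 24, reference within-subject SD 5.4 ms.

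**The plan's own figures.**
- Primary sample size, normal approximation: 2 × (8.5 × (1.645 + 1.282) / (10 − 4))² = 34.4, against 34 stated. An exact paired t-test needs 36, and its power at n = 34 is 88.6%. This is close enough to accept.
- Assay sensitivity: 5 / (1.24 × √24) = 0.82, as stated. An effect size of 0.62 at n = 30 gives 95.3% power. The SD limit is 5.4 × 0.82 / 0.62 = 7.1 ms, as stated.

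**What the stated rule does if sensitivity is lost.** This uses the simple paired t-test of Section 9.2, not the planned mixed model. The SD of the difference is 8.5 × √2 = 12.0 ms and the SE is 8.5 × √(2/34) = 2.06 ms. The rule passes when the mean difference + 1.692 × SE is below 10 ms. Moxifloxacin passes when its mean difference − 1.692 × SE is above 5 ms. The share of each true effect that is measured is an assumption. The last column comes from simulation with the placebo data shared by both comparisons.

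| Share measured | True drug effect → measured | Rule as written passes | Moxifloxacin (true 10 ms) passes | Both pass |
|---|---|---|---|---|
| 1 | 10 → 10 ms | 5% | 77% | about 2% |
| 0.75 | 10 → 7.5 ms | 32% | 32% | about 5% |
| 0.5 | 10 → 5 ms | 77% | 5% | about 2% |
| 0.5 | 12 → 6 ms | 60% | 5% | about 1% |

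For the last row, treating the two tests as independent gives 0.60 × 0.05 = 3%. The shared placebo lowers this, because a high placebo value helps the drug pass and hinders moxifloxacin.

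**Noise as a rival explanation.** With no attenuation and n = 34, raising the SD from 8.5 to 12 and 15 ms leaves the pass rate for a true 10 ms effect at 5%. For a true 12 ms effect the rate goes from 0.5% to 1.0% and 1.4%. For a 4 ms effect it falls from 89% to 65% and 49%. Noise widens the interval and pushes towards not excluding 10 ms.

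**Power for the joint claim** (true effects 4 ms for the drug and 10 ms for moxifloxacin, SD 8.5 ms, n = 34).
- Primary test alone: 88.6%.
- Moxifloxacin by the protocol's effect-size scaling: 0.823 × 5.4 / 8.5 = 0.523, which gives 91.0% power. Joint power if independent is 0.886 × 0.910 = 81%. It cannot be below 0.886 + 0.910 − 1 = 80%, nor above 89%.
- Moxifloxacin by the simple paired t-test: 76.7% power. Joint power with shared placebo, by simulation, is about 66%.

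**The case against.** The strongest case is that nothing in the analysis itself is wrong. The assay-sensitivity test is pre-specified, with its own hypothesis, its own sample-size argument and a two-part criterion. A failure would be reported beside the primary result, and a careful reader would discount the negative. That stands: a reader might infer that a failed control would be hidden, or that the test is missing, and the protocol supports neither. What is missing is the link between the two results.

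A reader might also infer that a noisy trial would produce a false claim of safety. It would not, as the working shows. Likewise, a baseline error common to all periods cancels in the placebo-corrected effect. Only attenuation of true effects causes the harm described.

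The attenuation factors and the true effects of 10 and 12 ms are assumptions. Nothing in the protocol says that sensitivity will be lost, so the percentages illustrate the rule's behaviour and do not forecast this trial.

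A separate statistical analysis plan, which is not at hand, might supply the link. Section 9.4.1.1 defers detail on heart-rate correction to such a plan. Sections 9.4.1.2 and 9.4.1.5 defer nothing on this point: the protocol states the conclusion rule in full, so an added condition would change a stated rule.

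Finally, requiring both results costs power. This objection stands, and the cost belongs with the fix.

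**Conclusion.** The point holds. The protocol fixes the conclusion of no clinically relevant prolongation on the upper bound alone and gives a failed moxifloxacin test no consequence, although Section 4.2 says that "a positive-control group will be utilized to establish assay sensitivity". Under an assumed halving of measured effects, with n = 34, SD 8.5 ms and a paired t-test, a true 10 ms effect would be declared clean in about 77% of trials under the rule as written and about 2% if assay sensitivity were also required. For a true 12 ms effect the figures are about 60% and about 1%.

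It would be tempting to add that the risk of a failed positive control is already covered by the sample size. Section 9.2 does not support that. Its 95% power for moxifloxacin holds only up to a within-subject SD of 7.1 ms, whereas the primary calculation uses 8.5 ms, and no joint claim is sized.

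**What to change.** In Section 9.4.1.2, make the concluding sentence conditional: the conclusion is drawn only if assay sensitivity has been demonstrated under Section 9.4.1.5 and the upper bound is below 10 ms. Add one sentence: if assay sensitivity is not demonstrated, the predicted effects and their CIs are reported, but exclusion of a 10 ms effect is not claimed. No alpha adjustment is needed, because both conditions must hold.

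The wording change is two sentences. The real cost is that the trial can end inconclusive when moxifloxacin fails by chance. Section 9.2 should therefore state the power of the joint claim and the method behind it. At SD 8.5 ms and n = 34 it is about 81% with the protocol's effect-size scaling for moxifloxacin, or about 66% by the simple paired t-test with shared placebo, against about 89% for the primary test alone. The rule and its power should be settled before any Part 2 data are unblinded.
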